## **12.2 Accrual and Feasibility**

### **Sample Size**

We will assess the dropout rate to inform us regarding the design of a subsequent randomized study. We will test the null hypothesis that retention  $< 65\%$  versus the alternative hypothesis that retention  $\geq 65\%$ , with 90% power for detecting an alternative retention of 80%. The 65% threshold is related to retention rate, and is different from the 75% of doses required for compliance (Section 12.1). Assuming a 1-sided test at the 0.05 significance level, we obtain a sample size of 75 participants. The sample size calculation was conducted using NQuery Advisor v7.0. Based on this calculation, we will plan for a sample size of 75, which will allow us to determine with a high level confidence whether or not the retention rate is sufficient to justify a subsequent study to this pilot.

We will also estimate the effect size in terms of reduction in neurocognitive decline in the intervention group as compared to historical controls. No formal statistical hypothesis will be tested for the purpose of declaring efficacy. The effect size, along with the estimate of the dropout rate, will be used to power and assess the feasibility of a planned subsequent randomized study. We expect an accrual rate of approximately 4 per month based on prior NCORP studies in similar brain tumor populations.

## **12.3 Primary Objective, Endpoint(s), Analysis Plan**

The primary objective of this study is to assess the retention rate of patients at 10 weeks of Ramipril treatment (6 weeks during RT and 4 weeks post RT) defined by compliance with drug therapy for at least 75% of doses during the 10 week period and completion of the composite neurocognitive battery. The retention rate will be estimated by count and percentage with corresponding 95% exact binomial confidence interval. All patients receiving at least one treatment of Ramipril will be evaluable for retention.

Additionally, the Clinical Trial Battery Composite Score is derived from the arithmetic mean of the standardized scores from the HVLt-R total recall, HVLt-R Delayed Recall, HVLt-R Delayed Recognition Discriminability, Trail Making Test Part A, Trail Making Test Part B, and COWA. For CTB COMP, the effect size of neurocognitive change of patients receiving Ramipril versus patients who do not receive Ramipril in patients with newly diagnosed GBM using the control arm of RTOG 0825 as the comparison group will be calculated with a corresponding 95% confidence interval.

## **12.4 Secondary Objectives, Endpoints, Analysis Plans**

All patients treated with at least one administration of Ramipril will be considered as intent to treat in secondary analyses, although we do realize missing data may be a factor if many do not complete repeated neurocognitive assessments over the study duration. Per protocol analyses will also be performed for those successfully retained as defined in the primary objective.

Since patients will not be randomized in this study, all secondary analyses will consider adjusting for covariates that differ between the patients enrolled and the comparison cohort in RTOG 0825. Pre-specified covariates will include MGMT methylation, KPS, and extent of resection. While this study will not be used to declare efficacy, we will use repeated measures analysis of covariance (RMANCOVA) models to explore the effect of Ramipril across time and to determine if the baseline characteristics moderate the treatment effects. Pairwise interactions with treatment will be assessed. Residuals will be assessed to determine if the model assumptions (linearity, homogeneity of variances and normality) are met, and transformations will be used if necessary. Additionally, multiple imputation under various assumptions regarding the missingness will be used in conjunction with the mixed effects models to assess how sensitive our results are to our missingness assumptions.

Treating physician response rate will be summarized at each timepoint with corresponding 95% confidence intervals. Time to neurocognitive failure will largely follow the method reported in Gilbert *et al.* for evaluating if there is meaningful difference in the risk of cognitive progression. Neurocognitive failure will be defined as the first decline on reliable change index on any of the individual cognitive tests. In the presence of competing risks for neurocognitive failure, including GBM-related mortality risk, we plan to explore the use of competing risks methods for both descriptive statistics (e.g. the Kaplan-Meier curves) and competing risk regression analysis. Competing risk methods are needed because time to neurocognitive failure is not independent of mortality and ignoring events from competing risk will lead to biased results. The competing risk analysis will be based on the method proposed in Gray and Fine and Gray using SAS macro %CIF and PROC PHREG. Patient reported outcomes will be assessed as described above for the CTB COMP.

Exploratory subgroup analyses will be conducted for all 4 month post RT outcomes by whether the patient received Optune® (also known as Tumor-Treating Fields or TTFIELDS) as part of their standard treatment following RT. Differences by Optune® for continuous outcomes will be assessed by two-sample t-tests where parametric assumptions hold; otherwise Mann-Whitney U tests will be applied. For categorical outcomes, Fisher's exact or Chi-square tests will be implemented. Corresponding 95% confidence intervals will also be presented for outcomes within each subgroup.

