Cognitive reserve (CR) refers to acquired compensatory strategies that enhance a person's cognitive and behavioral capacities. Individuals with higher CR should have less impairment because of their greater adaptive capacity. Common proxies for CR are literacy and educational and occupational attainment. Higher levels of CR have been associated with lower incident rates of age-associated cognitive impairment and longer delayed onset of dementia. CR will be examined as a susceptibility factor for RICD (we hypothesize that low CR individuals will have greater cognitive impairment at baseline than higher CR individuals).

In summary, RICD is a common problem following brain RT for GBM. It can affect various cognitive functions, and generally does not have a plateau in terms of severity after onset. Preclinical models suggest that by modifying the RAS within the brain, one can mitigate the inflammatory cascade that ultimately leads to RICD. Ramipril is a widely used safe and tolerable ACE-I that penetrates the blood brain barrier. The Wake Forest NCORP Research Base has a long history of evaluating pharmaceutical interventions that may mitigate symptoms of RICD, demonstrating our ability to conduct this current study. This proposal represents collaboration between Wake Forest investigators and the neurocognitive experts involved in the RTOG 0825 study. RTOG 0825 was a prospective, randomized phase III trial in newly diagnosed patients with glioblastoma comparing standard radiation and temozolomide therapy with

and without bevacizumab. RTOG 0825 also prospectively collected extensive neurocognitive data on all enrolled patients. The eligibility criteria and planned combined modality treatment proposed in this trial are identical to that used for the cohort of patients treated on the control arm of RTOG 0825.

Furthermore, the neurocognitive battery and times of administration proposed in this study have been harmonized with the battery and schedule utilized in RTOG 0825 thus providing an ideal modern era historical control group to appropriately compare with this pilot study population and ensure an ability to interpret the results of our proposed trial in the context of the most current understanding and effect magnitude of RICD in the GBM population.

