Comprehensive Metabolic Panel (CMP): Inclusive of creatinine, potassium, GFR, Total Bilirubin, AST and ALT. Labs are required within 14 days of enrollment. These labs should also be collected at Baseline, Weeks 1-6 during RT and at 1 Month Post RT (Wk 10). Refer to Section 5.5 for criteria for Dose Modifications related to labs. The CMPs for Week 1, 2, 3, 4, 5 & 6 during RT should be analyzed through LabCorp and paid by the study directly to LabCorp. If local sites perform CMPs at Week 1, 2, 3, 4, 5 or 6 during RT as standard of care, these values can be used to determine toxicity, but LabCorp CMPs should also be drawn for consistence across study sites. Sites should choose if LabCorp or local institutional lab values will be used to assess drug related toxicity that determines if dose escalation per protocol is appropriate during weeks 1-6 of RT. The same lab should perform the CMPs for Week 1-6 visits. At Baseline and 1 month post RT, standard of care local labs should be used for the study and to determine toxicity, if applicable.

In the event of inability to obtain LabCorp results in an appropriate time interval, local standard of care labs can be used for Ramipril titration decision making and other protocol related activities.

If lab abnormalities are detected that would affect the conduct of the study, treating physicians should consider whether correctable disease or treatment related toxicities (e.g. dehydration, nausea and vomiting, etc.) could be responsible. If so, clinicians should attempt to address those issues and repeat the labs within 24-48 hours for protocol decision making.

ECOG (Eastern Cooperative Oncology Group) Performance Status: Study Team should determine the patient's ECOG performance status using the chart in Appendix A at the Baseline visit.

Serum or Urine  $\beta$ HCG: A negative serum or urine pregnancy test is required within 14 days prior to enrollment for women of childbearing potential. Results will be used from standard of care local labs.

APOE Genotyping: At Baseline, a blood vial of approximately 8 ml will be taken from a vein in the arm/central line for lab analysis. Blood samples will be stored with a unique identifier and will not include any information protected by HIPAA regulations. Blood samples will be stored at Wake Forest. See Section 9.0 for specimen management.

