### 8.2 Secondary Endpoints

**Participant reported outcomes (PRO):** Participant-reported outcomes will complement the neurocognitive battery. The EORTC Quality of Life Questionnaire-Core 30/Brain Cancer Module-20 (EORTCQLQ30/BN20) will measure several domains of functioning (physical, emotional, cognitive, social, fatigue, pain, etc.) (8 minutes). Each cognitive test and PRO proposed has adequate psychometric properties and has been used previously in clinical trials of oncology patients.

**Imaging:** Adequate imaging for diagnostic, treatment planning and follow-up imaging will follow standard of care practices and will include contrast-enhanced T1-weighted MRI and T2 or FLAIR imaging. Contrast-enhanced CT will be allowed only in cases where patients are unable to undergo MRI because of non-compatible devices. MRI of the brain will be performed 1- and 4-month post-RT or until time of tumor progression, should that occur prior to the 4-month post-RT time point. Response assessment will be based on treating investigator assessment and institutional standard of care. Imaging parameters will only be utilized to measure response and progression.

**Other variables to be measured:** Sociodemographic variables to be assessed in a questionnaire at baseline will include age, education, race/ethnicity, menopausal status, co-morbid medical conditions, concomitant medication, marital status, socioeconomic status, tumor size and location. Variables to be assessed after completion of each treatment phase by treating physician include dates, dose and compliance of temozolomide administration, radiation dose, radiation dose per fraction, and radiation volume (e.g. planned treatment volume (PTV)). *Cognitive reserve* (CR) will be measured with the Shipley Scale-Vocabulary with educational (years in school) and occupational attainment (standardized 8-level classification) also measured as proxies for CR.

**Biomarkers:** APOE genotype, a risk factor for cognitive impairment and dementia, will be derived from

whole blood samples taken at baseline at the site of study enrollment. See Section 10.1 for sampling handling and processing.

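### No covariate adjustment is specified for the primary 10-week CTB COMP effect size against RTOG 0825, and the covariates named for the secondary analyses are not listed for collection in that form

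*Combined protocol and SAP*

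**What the plan says.** Objective 1.1.2 and section 8.1 make CTB COMP at 10 weeks a primary endpoint. Section 12.3 describes the estimate as "the effect size of neurocognitive change of patients receiving Ramipril versus patients who do not receive Ramipril", with the RTOG 0825 control arm as comparator and a 95% confidence interval. It names no model, baseline term, covariate or matching. Section 12.2 says that this effect size, together with the dropout estimate, will be used to power the next randomised study and judge its feasibility. It also says that no test will be made to declare efficacy.

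Adjustment first appears in section 12.4. Because patients are not randomised, "all secondary analyses will consider adjusting for covariates that differ between the patients enrolled and the comparison cohort in RTOG 0825". The next sentence fixes a minimum list: "Pre-specified covariates will include MGMT methylation, KPS, and extent of resection". A repeated-measures analysis of covariance follows.

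On data collection, section 7.3 states "Study Team should determine the patient's ECOG performance status", using the ECOG chart in Appendix A. Section 8.2 lists the baseline questionnaire variables as "age, education, race/ethnicity, menopausal status, co-morbid medical conditions, concomitant medication, marital status, socioeconomic status, tumor size and location". On comparability, section 2.2 calls the eligibility criteria and planned treatment "identical to that used for the cohort of patients treated on the control arm of RTOG 0825".

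**The concern.** The reason section 12.4 gives for adjusting, that patients are not randomised, applies equally to the primary estimate in section 12.3. Yet section 12.3 says nothing about adjustment, and section 12.4 makes it optional and confines it to secondary analyses. Beyond three named covariates, section 12.4 would choose by observed differences between the cohorts. That leaves the choice open until the data are in hand.

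The named list also does not match the listed data. An analyst who followed the plan would find no listed source for MGMT or KPS and no listed field for extent of resection. Two factors that the protocol itself links to cognitive vulnerability are not on the list.

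What is at stake is the size of the next trial. A difference between cohorts in patient mix would pass into the planning effect size, and the confidence interval would not show it.

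**Working it through.** **1. The plan's own figure.** The only powered quantity is retention: "Assuming a 1-sided test at the 0.05 significance level, we obtain a sample size of 75 participants". Inputs from section 12.2 are null 65%, alternative 80% and power 90%.

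n = [(1.645·√(0.65·0.35) + 1.2816·√(0.80·0.20)) / 0.15]² = 74.78, rounded up to 75.

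The exact rule of at least 56 of 75 retained has one-sided alpha 0.0485 and power 90.03%. The stated N reproduces. It does not depend on CTB COMP, so nothing below changes it.

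**2. Covariates against listed data.** Sources are the schedule of events (7.1), sections 4.1, 7.3 and 8.2, and the Appendix B checklist.

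| Factor | Pre-specified in 12.4 | Listed for collection |
|---|---|---|
| MGMT methylation | Yes | No; named only in 12.4 |
| KPS | Yes | No; named only in 12.4. ECOG is recorded at baseline |
| Extent of resection | Yes | Not a listed data item. Partial or gross total resection is an eligibility condition (4.1.1), and post-operative scan reports must be submitted (4.1.7) |
| Baseline cognition | No | Yes; the component tests are given at baseline (7.1) |
| Age | No | Yes (8.2) |

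Section 2.2 names older age and lower baseline cognitive performance as possible markers of greater risk of cognitive decline.

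**3. How large a bias could be.** The documents give no CTB COMP standard deviation, expected effect, RTOG 0825 control number or covariate imbalance, so the actual bias cannot be computed. Every value in this step and the next is assumed.

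Bias from one binary factor = difference in prevalence × effect in SD. A 10 to 30 point difference and a 0.2 to 0.6 SD effect give 0.02 to 0.18 SD. For example, 0.20 × 0.5 = 0.10 SD.

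**4. Effect on the next trial** (two arms, SD = 1, two-sided 5%, 90% power).

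n per arm = 2(1.96 + 1.2816)² / d²

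- d = 0.30: 21.016 / 0.09 = 233.5, so 234.
- d = 0.20: 21.016 / 0.04 = 525.4, so 526.

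Power with 234 per arm if the true d is 0.20: Φ(0.20·√(234/2) − 1.96) = Φ(0.203) = 58%.

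| Observed d (n per arm) | Of which bias | True power | n per arm needed |
|---|---|---|---|
| 0.30 (234) | 0.05 | 77% | 337 |
| 0.30 (234) | 0.10 | 58% | 526 |
| 0.40 (132) | 0.05 | 81% | 172 |
| 0.40 (132) | 0.10 | 68% | 234 |
| 0.40 (132) | 0.20 | 37% | 526 |

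The direction is unknown. If 0.30 were observed and 0.40 were true, the next trial would be planned at 234 per arm when 132 would do.

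**5. Sampling error, for scale.** SE(d) = √(1/n₁ + 1/n₂ + d²/(2(n₁+n₂))) at d = 0.30, with 60 evaluable ramipril patients and 100 to 300 controls (both assumed). The SE is 0.164 to 0.142, so the 95% half-width is 0.32 to 0.28 SD.

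**The case against.** Several stronger readings are tempting, and the documents do not support them.

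- **That the primary comparison is planned as unadjusted.** Section 12.3 is silent, which is not the same thing. Section 12.4 says that patient-reported outcomes will be handled in the way set out above for CTB COMP, and section 12.5 proposes mixed models for the data generally. Both hint that the modelled analysis may cover CTB COMP. What remains is that no text says so, and none says which estimate will be used for planning.
- **That MGMT and KPS are not collected.** The Baseline Data Collection Form is named in Appendix B, but its fields are not shown. Only absence from the listed items can be stated.
- **That the adjustment cannot be run.** Extent of resection could be recovered from eligibility records and scan reports, and ECOG can stand in for KPS given a mapping. The list in section 12.4 is also not worded as exhaustive.
- **That the estimate is confounded.** No imbalance is documented. The protocol asserts identical eligibility, which would lessen the risk. It would not remove it, because patient mix can differ within the same criteria. Some criteria here are specific to ramipril, such as those on ACE-inhibitor intolerance, low systolic pressure, potassium and solitary kidney. The RTOG 0825 criteria are not in the documents, so the assertion cannot be checked.

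It can also be said that baseline and age are partly handled already. The estimate concerns change, and section 7.6.3 says the tests have norms that account for age. But the plan does not say that those norms define the standardised scores. Subtracting baseline is also not the same as adjusting for it.

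Finally, sampling error of about 0.3 SD is some three times the illustrated bias of 0.10 SD and could by itself move the next trial from 234 to 526 per arm. That is true, and adjustment will not cure it. The confidence interval shows sampling error, however, and does not show bias.

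**Conclusion.** The point holds in this form: the primary 10-week CTB COMP effect size has no specified adjustment, the optional adjustment in section 12.4 rests on covariates that are not listed for collection as named, and two collected factors that the protocol considers relevant are not pre-specified. The estimate that feeds the next trial is open to confounding of unknown size and direction.

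The shift from 234 to 526 per arm rests wholly on assumed inputs and illustrates sensitivity; it does not predict what will happen. Importance is moderate (should fix). No efficacy claim depends on the comparison, the retention endpoint is untouched, and N = 75 stands.

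**What to change.** - **Section 12.3:** make the planning estimate the adjusted difference in 10-week CTB COMP between the ramipril patients and the RTOG 0825 controls. Fix the covariates in advance rather than by observed imbalance: baseline CTB COMP, age, performance status, extent of resection and MGMT. Report the unadjusted figure second. With baseline in the model, the adjusted difference is the same whether the outcome is the 10-week score or the change, so the present aim is kept.
- **Baseline data items:** add MGMT result and extent of resection, taken from the chart, if the baseline form does not already hold them.
- **Performance status:** use one scale available in both cohorts. ECOG would serve, with a stated KPS mapping if RTOG 0825 recorded KPS.
- **Limits of the comparator:** use MGMT and resection only as far as the RTOG 0825 records hold them, which should be confirmed before the list is final.
- **Missing MGMT:** handle it by the multiple imputation already planned in sections 12.4 and 12.5, with wording that extends it to covariates. Keep an unknown category as a sensitivity analysis only, since it can leave residual confounding.

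The cost is statistical wording, two chart-abstracted fields and some missing MGMT results. Baseline CTB COMP, age and ECOG need no new data. The change should be made before the RTOG 0825 data are compared. It is also easier while patients are in follow-up, because section 4.4.1 ends data collection after the 5-month call.

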Optune® with adjuvant temozolomide in patients with newly diagnosed supratentorial glioblastoma is listed as a level 1 recommendation by the NCCN guidelines and has been adopted by many, but not nearly all, medical practitioners who treat these patients. Currently, a minority of newly diagnosed glioblastoma patients are either offered or choose to accept this treatment modality due to patient or provider preferences, or established contraindications to use which include the presence of implantable electronic devices, allergy to the array’s conductive hydrogel adhesive or the presence of cranial defects. Optune® may only be prescribed by qualified physicians who have completed a training course given by Novocure (the device manufacturer). Of note, as prescribed in the pivotal clinical trial referenced above, standard practice is to apply the Optune® device no sooner than 4 weeks after the completion of concurrent radiation and temozolomide chemotherapy.

For patients enrolled on this trial, Optune® may be used at the discretion of the treating physicians as per standard of care guidelines, timing and training. Use will be captured and an exploratory analysis of primary and secondary objectives based on the subgroups using and not using the device will be performed.

**Drug:** Ramipril (e.g. Altace® or Tritace®) is an ACE-I. It is currently FDA approved for use in the treatment of hypertension and for reducing the risk of myocardial infarction, stroke and death from cardiovascular causes. The drug will be obtained, packaged, and distributed by McKesson Corporation (Winston-Salem, NC). McKesson Corp. will also provide storage and inventory for the study drug. Ramipril will be provided to study participants at no cost.

**Assessment plan:** Participants will complete the entire battery of neurocognitive tests and questionnaires measuring cognitive symptoms, mood, fatigue, sleep disturbance and quality of life at baseline, at the completion of RT, 1 month post-RT, and q3 monthly thereafter up to 4 months post-RT or until time of

tumor progression. At the end of radiation and at the one and four-month post-RT follow-up visit, patients' tolerance of medication and compliance will be assessed by a research team member at an in-person visit coordinated with clinical follow-up. Patients are encouraged to call at any time for questions regarding study drug and will fill out a diary to document study drug compliance.

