- Following lack of significant toxicity (including laboratory and blood pressure) review after week 1, patients will take two 1.25 mg capsules of Ramipril (2.5 mg total) per day. Following lack of significant toxicity review after week 2, patients will take four 1.25 mg capsules (5 mg total) per day. The titration of the medication is expected to be complete within the first 3-4 weeks of RT and the Ramipril will continue at the same dose during the remainder of RT and for an additional four months after RT.
- Ramipril treatment may be terminated early if intercurrent illness occurs that prevents further administration, unacceptable adverse events occur, the patient decides to withdraw from the study or if changes in the patient's condition occur to render the patient unacceptable for further treatment in the judgment of the investigator. Refer to Section 8.3 Off-Agent for guidelines.
- Delays in radiation therapy will not affect Ramipril dose titration. If radiotherapy is delayed, the patient will continue on their current dose of Ramipril, or the dose of Ramipril could be reduced as per the above criteria if a significant toxicity occurred. If there is a delay in radiotherapy, patient would still continue Ramipril until 4-months post RT, which could mean the study visits may be pushed out the number of days of the delay. For example, if there is a 1 week RT delay, the patient would have the 1 month-Post RT visit at Week 11, instead of Week 10. A final toxicity assessment will be done by phone at 5 months post RT (Week 26).

If the patient misses a dose of study medication and if it is less than 4 hours late, have them take that dose of study medication as directed. If the patient misses a dose of study medication and if it is greater than 4 hours, do not have them take this dose. Have them take their regular dose at the usual time the following day. If more than one day is missed of study medication, please have them continue as soon as possible. Any missed doses of study medication should be documented on their patient diary.

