#### **Cognitive & PRO Testing:**

**Participant Related Outcomes Assessments (PRO) (EORTCLQ-30/BN20):** Study Team should administer at Baseline, RT Completion, 1- and 4- month post RT visits. *If patient goes Off-Study for any reason, the PRO should be administered.*

**Neurocognitive Assessments (HVLt-R, Trail Making Tests, Part A & B, COWAT and Shipley Institute of Living Scale):** The entire battery of neurocognitive tests and questionnaires will be administered by a trained and certified examiner. Refer to Section 7.6 for specifics. Note that the Shipley Institute of Living Scale will only be given at Baseline, while all others are also given at RT Completion, 1- and 4- Post RT visits. *If patient goes Off-Study for any reason, the entire next set of Neurocognitive Assessments should be administered, except the Shipley Institute of Living Scale.*

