#### 8.3.2 Off-Study Criteria

Participants may go 'off-study' for one or more of the following reasons: the protocol intervention and any protocol-required follow-up period is completed, AE/SAE, lost to follow-up, refusal to continue with study procedures, the need for contraindicated concomitant medication, medical contraindication, disease progression, withdraw consent, death, determination of ineligibility (including screen failure), pregnancy, or treating physician decision.

Note that a participant is not automatically taken off-study if they refuse further treatment. In fact, these participants should be encouraged to remain in the study and provide data at their regularly scheduled visits. Date and reason off-study should be documented on the Off Study case report form. Reasons that are not specified on the form should be coded as 'Other' and a brief description provided.

A final evaluation of the participant should be performed when he/she withdraws from the study. If a patient decides to discontinue participation in study at any time prior to study completion, the entire battery of neurocognitive tests and forms should be administered, using the next Neurocognitive and PRO booklet they would have received as well as, all other items in the Schedule of Events (Section 7.1) for the visit.

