Study hypotheses that will be explored include the following: 1) patient retention will be sufficiently high to proceed forward with a randomized trial of Ramipril; 2) patients receiving Ramipril will have better neurocognitive function (assessed using the Clinical Trial Battery Composite Score) compared to historical controls who did not receive Ramipril; 3) neurocognitive decline will be slower in patients receiving Ramipril; 4) patients receiving Ramipril will have better scores for the individual neurocognitive function tests; 5) patients receiving Ramipril will have better mood and quality of life and less fatigue and sleep disturbance.

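### Time to neurocognitive failure is seen only when the battery is given, but Section 12.4 names only continuous-time methods, so a visit-timing difference from RTOG 0825 can bias the hazard ratio in either direction

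*Combined protocol and SAP*

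**What the plan says.** Section 12.4 defines the event: "Neurocognitive failure will be defined as the first decline on reliable change index on any of the individual cognitive tests". Objective 1.2.1 agrees. Section 12.1 ties decline to the composite score instead, but on either definition it is visible only when the battery is given.

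The schedule in Section 3 is "at baseline, at the completion of RT, 1 month post-RT, and q3 monthly thereafter up to 4 months post-RT". Section 7.3, setting aside the baseline-only vocabulary scale, says "all others are also given at RT Completion, 1- and 4- Post RT visits". Section 7.1 labels the post-baseline batteries Weeks 6, 10 and 22. Section 7.2 allows 3 days either way at Week 6 and 7 days either way at Weeks 10 and 22. Visits follow radiotherapy: "if there is a 1 week RT delay, the patient would have the 1 month-Post RT visit at Week 11" (Section 5.2, and the notes to Section 7.1). There is also an unscheduled battery for patients who leave early: "the entire battery of neurocognitive tests and forms should be administered, using the next Neurocognitive and PRO booklet they would have received" (Section 8.3.2).

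For the analysis, Section 12.4 says "we plan to explore the use of competing risks methods", naming Gray and Fine-Gray "using SAS macro %CIF and PROC PHREG". It gives no time origin, no event-dating rule, no censoring rule for patients without decline, and no interval-censored or discrete-time method.

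The comparator is the RTOG 0825 control arm. Section 2.2 says battery and schedule were harmonised with that trial, but gives none of its actual visit dates, windows or delay rules.

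**The concern.** The true date of decline is unknown; only the two batteries that bracket it are known. The gaps are about 6, 4 and 12 weeks, while death, the competing event, can fall on any day. A continuous-time model takes the detection date as the event date, so it compares when patients were tested as well as when they declined. Under randomisation the testing pattern would balance on average. Against an external cohort it need not.

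The estimate matters even though no efficacy claim is planned. Time to decline is secondary objective 1.2.1, and Section 12.1 lists among the hypotheses to be explored that "neurocognitive decline will be slower in patients receiving Ramipril". Section 12.2 will use the effect size for neurocognitive decline against historical controls to power the next, randomised trial. A hazard ratio that partly reflects the visit calendar could colour that decision.

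**Working it through.** The plan states no figure for this endpoint. Its sample size of 75 concerns retention only, so there is nothing to reproduce.

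**1. Inputs.** From the documents: visits at Weeks 6, 10 and 22; the Section 7.2 windows; 75 Ramipril patients; decline in about 30% within four months of radiotherapy (Section 2.1). Assumed: 300 controls, 10% deaths by Week 22, constant hazards, and 50% decline as a second case because failure on any one test counts.

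**2. Where the bias arises.** With 30% decline by Week 22 and deaths ignored, the weekly hazard is −ln(0.70)/22 = 0.0162. The chance of decline in each interval, given none before, is:
- to Week 6: 1 − exp(−6 × 0.0162) = 0.093
- Week 6 to 10: 1 − exp(−4 × 0.0162) = 0.063
- Week 10 to 22: 1 − exp(−12 × 0.0162) = 0.177

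About 0.907 × 0.937 = 0.85 reach Week 10 without decline, and 0.85 × 0.177 = 0.15. So half of the 30% are detected at the last battery.

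Now take two equal cohorts with no true difference, all controls tested just before all Ramipril patients.
- *Week 6.* Control events occur with both cohorts at risk (Ramipril share 1/2). Ramipril events occur after 9.3% of controls have left (share 1/(2 − 0.093) = 0.524). Expected over observed Ramipril events is 0.500 + 0.524 = 1.02, a trivial bias.
- *Week 22, event-free patients censored at their own visit.* Control events occur while every Ramipril patient is still at risk. By the time Ramipril events occur, no controls remain, so those events carry no information. This visit alone would push the ratio towards zero. Windows overlap in practice, which softens this.
- *Week 22, everyone kept at risk to one common date.* The ratio is 0.500 + 1/(2 − 0.177) = 0.500 + 0.549 = 1.05, a small bias.

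Reversing the testing order reverses the direction.

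**3. Simulation with no true effect.** Visit dates are uniform within the windows, decline is dated at the next battery, and deaths stay in the risk set. The repeat used 400 runs per case. Entries are Fine-Gray hazard ratios with event-free patients censored at their own last visit; ranges cover the decline rates tried.

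| Ramipril batteries relative to controls | HR | Repeat |
|---|---|---|
| Same timing | 0.97–1.02 | 0.99–1.00 |
| 3.5 days later on average | 0.61–0.63 | 0.60–0.63 |
| 3.5 days earlier on average | 1.41–1.47 | 1.41–1.42 |
| 25% of Ramipril, no controls, 7 days late | 0.74–0.78 | 0.75–0.80 |
| 25% v 15% 7 days late | 0.93–0.94 | 0.90–0.92 |
| 25% v 25% 7 days late | 0.98–1.00 | 1.00 |

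With a common horizon, the hazard ratio is 0.94–1.01 even for a 7-day shift.

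**4. Visit-scale model.** A complementary log-log model with one term per visit interval gave 0.96–1.05 across these cases.

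**5. Control follow-up.** If controls are also tested beyond Week 22 (Week 34 assumed) and not truncated, the hazard ratio is 1.27–1.50 with no timing shift, a bias against Ramipril.

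**The case against.** A reader might infer that pushing visits out with radiotherapy delay makes decline look slower on Ramipril. The documents do not support that. Visits move because they are anchored to the end of radiotherapy. Section 3 says chemoradiotherapy follows the RTOG 0825 standard arm, Section 2.2 says the test schedule was harmonised, and nothing says controls were handled differently. The windows are symmetric and create no average shift by themselves. Section 5.1.1.2 recommends keeping interruptions below 8 days. When both cohorts have delays, the bias is modest or absent.

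The large ratios also depend on a censoring convention that the plan does not state; a common horizon nearly removes them. But censoring at last assessment is an ordinary default, so an unstated coding choice decides whether a null effect reads near 1.0 or well away from it.

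It would be too strong to say that a hypothesis is tested here. Section 12.4 explores these methods, and Section 12.2 rules out a formal efficacy test. Nor do the documents support a complaint about tied event times, since no tie method is named.

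Section 12.4 says the approach will largely follow a published report, which may code by visit. That cannot be seen from the documents, and the SAP should not depend on it.

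What stands is that dating, censoring and visit alignment are unspecified for a comparison with an external cohort.

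**Conclusion.** The point holds as a direction-neutral weakness in an exploratory secondary analysis. Failure is interval-censored, the named methods treat detection dates as exact, and the comparator is not randomised. A systematic difference of a few days can move a null hazard ratio to about 0.6 or to 1.4–1.5 under own-last-visit censoring. A more moderate imbalance, 25% against 15% of patients delayed a week, moves it to roughly 0.9. Equal timing gives no bias.

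These sizes rest on the assumed control number, death rate, decline rates and constant hazards. The actual RTOG 0825 visit dates are not in the documents, so neither the direction nor the size of any real shift is known. It is worth correcting because the remedy is cheap and the estimate will inform the next trial.

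**What to change.** Amend Section 12.4 as follows.
- Analyse neurocognitive failure by visit interval: baseline to end of RT, end of RT to 1 month post RT, and 1 to 4 months post RT.
- Fit a grouped-time complementary log-log competing-risk model with a term for each interval, keeping patients who die without observed decline in the later denominators.
- Assign an off-study battery to the interval of the booklet used. Section 8.3.2 already has the site use the next scheduled booklet, so this needs no new rule at sites.
- Report cumulative incidence at the three nominal visits.
- Apply identical coding to the RTOG 0825 controls, truncated at 4 months post RT.
- Tabulate actual battery dates by cohort, so that any timing difference is visible. The RTOG 0825 data request should therefore include visit labels and assessment dates.

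The cost is SAP wording and slightly different code, with no new data collection in this trial. The output becomes three incidence points instead of a continuous curve, which loses little because decline is observed at little more than three times.
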